#### **7.3.3.2 Assessment**

Different species or strains of MAC than those that are identified post Baseline (Day 1) after culture conversion will be recorded in source data.

#### **7.3.4 Computed Tomography Scan of Chest**

Chest CT scans will be evaluated as part of the chest CT Scan Sub-Study at sites that are willing and have been approved for the sub-study. The objective this sub-study will be to compare assessments of the chest CT scans, read by a trained medical professional, from Baseline (Day 1) to the (EOT) visit ( $\pm 14$  days) provided a chest CT scan was not obtained within the prior 6 months. High resolution CT scan is preferred, if available. Details regarding the chest CT Scan Sub-Study are described in [APPENDIX 4](#). Details of the Japan specific CT Scan Sub-Study are described in [APPENDIX 5](#).

#### **7.3.5 All-cause Mortality**

##### **7.3.5.1 Methodology**

Study staff will make every effort to determine the vital status of subjects who do not complete the EOS visit.

##### **7.3.5.2 Assessment**

The cause of death, if available, for subjects that do not survive 12 months beyond EOT or early discontinue during the study will be recorded in the eCRF.

Protocol Amendment #3 version: 22 February 2016

*This protocol is solely for the purpose of communicating information about the investigational drug between Insmmed Incorporated and study personnel. Information is not to be reproduced, abstracted or used for sharing of information for any other purpose, whatsoever, except with the written permission of Insmmed Incorporated.*

## 7.4 PHARMACOKINETICS

### 7.4.1 Methodology

**Population PK Sub-Set (US and Japan Only):** Blood and sputum samples will be collected to determine amikacin concentrations, one from 0 to 1 hour before and one from 1 to 4 hours after study drug administration at Months 1, 3, and 6 in at least 16 evaluable US subjects randomized to the LAI treatment arm at pre-selected sites. In addition, at least 8 evaluable Japanese subjects randomized to the LAI treatment arm will participate in the population PK assessment.

**Sputum-Only PK Sub-Set:** An additional sub-set of subjects in the LAI added to a multi-drug regimen arm (at least 60 subjects) will have sputum samples collected to assess residual amikacin concentration in sputum after interrupting/stopping LAI treatment at the various different time points: Baseline, Months 4, 5 and 6 (2 days interruption of LAI dosing), 28 days and 3 months off-treatment.

All samples will be stored at or below  $-20^{\circ}\text{C}$  before shipping to a central PK laboratory. Details for collecting, handling, storing, and transporting blood and sputum samples for PK analyses will be provided in the site laboratory manual.

### 7.4.2 Sample Collection

All sample handling procedures, including the date and time of each sample collection will be documented in the eCRF. The time of placement into storage (at the end of the sample work-up), and the date of transfer or shipment of the samples to the responsible analyst will be collected in the source documents. .

### 7.4.3 Comprehensive Pharmacokinetic Sub-Study (Japanese sites only)

PK of LAI in serum and sputum will be determined at pre-defined time points for the first 6 months in at least 8 evaluable Japanese subjects who have been randomized to the LAI plus a multi-drug regimen arm. The objectives will be to characterize the PK, including bioavailability, and systemic exposure of LAI, compare to historical population PK results, and to evaluate the

Protocol Amendment #3 version: 22 February 2016

*This protocol is solely for the purpose of communicating information about the investigational drug between Insmmed Incorporated and study personnel. Information is not to be reproduced, abstracted or used for sharing of information for any other purpose, whatsoever, except with the written permission of Insmmed Incorporated.*

concentration of LAI in the sputum for Japanese subjects with NTM lung disease. Refer to [APPENDIX 3](#)

Protocol Amendment #3 version: 22 February 2016

*This protocol is solely for the purpose of communicating information about the investigational drug between Inmed Incorporated and study personnel. Information is not to be reproduced, abstracted or used for sharing of information for any other purpose, whatsoever, except with the written permission of Inmed Incorporated.*

Confidential

[COMPREHENSIVE PHARMACOKINETIC SUB-STUDY](#) for details.

#### **7.4.3.1 Comprehensive Pharmacokinetic Sub-Study Sample Collection**

All sample handling procedures, including the date and time of each sample collection. The time of placement into storage (at the end of the sample work-up), and the date of transfer or shipment of the samples to the responsible analyst will be collected in the source documents.

### **7.5 HEALTH CARE RESOURCE UTILIZATION**

The number of days missed from work, NTM related and non-NTM related visits to healthcare providers, Emergency Room (ER) visits, and hospitalizations including days in the hospital, and days in Intensive Care Units (ICU) will be captured at every visit except Month 10, 14, and off-treatment visits.

### **7.6 APPROPRIATENESS OF MEASUREMENTS**

Data will be collected using standard methods, widely used and generally regarded as reliable accurate, and relevant.

## **8 ADVERSE EVENTS**

The Investigator is responsible for the detection and documentation of events meeting the criteria and definition of an AE or SAE as provided in this protocol.

### **8.1 DEFINITION OF AN ADVERSE EVENT**

Any untoward medical occurrence in a subject or clinical investigation subject administered a pharmaceutical product and which does not necessarily have to have a causal relationship with this treatment.

An AE can therefore be any unfavorable and unintended sign (including an abnormal laboratory finding, for example), symptom, or disease temporally associated with the use of a medicinal product, whether or not considered related to the medicinal product.

Examples of AEs include one of the following or a combination of 2 or more of these factors:

Protocol Amendment #3 version: 22 February 2016

*This protocol is solely for the purpose of communicating information about the investigational drug between Insmmed Incorporated and study personnel. Information is not to be reproduced, abstracted or used for sharing of information for any other purpose, whatsoever, except with the written permission of Insmmed Incorporated.*

- A new sign, symptom, illness, or syndrome
- Worsening of a concomitant illness
- An effect of investigational product, including comparator or concomitant medication
- An effect of an invasive procedure required by the protocol
- An accident or injury
- Laboratory abnormality that the Investigator considers clinically relevant

Surgical procedures themselves are not AEs; they are therapeutic measures for conditions that require surgery. The condition for which the surgery is required is an AE, if it occurs or is detected during the study period. Surgical measures planned prior to study enrollment are permitted by the clinical study protocol and the condition(s) leading to these measures are not AEs.

## 8.2 DEFINITION OF A SERIOUS ADVERSE EVENT

A serious adverse event (experience) or reaction is any untoward medical occurrence that at any dose:

- results in death,
- is life-threatening,
  - NOTE: The term "life-threatening" in the definition of "serious" refers to an event in which the subject was at risk of death at the time of the event; it does not refer to an event which hypothetically might have caused death if it were more severe.
- requires inpatient hospitalization or prolongation of existing hospitalization,
- results in persistent or significant disability/incapacity, or
- is a congenital anomaly/birth defect.

Medical and scientific judgment should be exercised in deciding whether expedited reporting is appropriate in other situations, such as important medical events that may not be immediately life-threatening or result in death or hospitalization but may jeopardize the subject or may require

Protocol Amendment #3 version: 22 February 2016

*This protocol is solely for the purpose of communicating information about the investigational drug between Insmmed Incorporated and study personnel. Information is not to be reproduced, abstracted or used for sharing of information for any other purpose, whatsoever, except with the written permission of Insmmed Incorporated.*

intervention to prevent one of the other outcomes listed in the definition above. These should also usually be considered serious.

Examples of such events are intensive treatment in an emergency room or at home for allergic bronchospasm; blood dyscrasias or convulsions that do not result in hospitalization; or development of drug dependency or drug abuse. . The IB serves as the Reference Safety Information for the determination of expectedness of AEs. Investigators should reference the current IB when assessing the expectedness of adverse reactions for reporting to Health Authorities/IRB/Independent or Institutional Ethics Committee (EC)/Investigators.

### 8.2.1 Assessment of Intensity

Each AE will be graded according to CTCAE v4.0, as applicable. All other laboratory and clinical AEs that occur in a subject will be assessed for severity and classified using the categories below.

- **Grade 1 (Mild):** Event requires minimal or no treatment and does not interfere with the subject's daily activities.
- **Grade 2 (Moderate):** Event results in a low level of inconvenience or concern with the therapeutic measures. Moderate events may cause some interference with functioning.
- **Grade 3 (Severe):** Event interrupts a subject's usual daily activity and may require systemic drug therapy or other treatment. Severe events are usually incapacitating.
- **Grade 4 (Life threatening):** Any adverse drug experience that places the subject, in the view of the Investigator, at immediate risk of death from the reaction as it occurred (i.e., it does not include a reaction that had it occurred in a more severe form, might have caused death).
- **Grade 5 (Death)**

Protocol Amendment #3 version: 22 February 2016

*This protocol is solely for the purpose of communicating information about the investigational drug between Insmmed Incorporated and study personnel. Information is not to be reproduced, abstracted or used for sharing of information for any other purpose, whatsoever, except with the written permission of Insmmed Incorporated.*

### 8.2.2 Assessment of Causality

The Investigator who identifies an AE will determine the causality of each based on the temporal relationship to administration of study drug and clinical judgment. The degree of certainty about causality will be graded using the categories below.

**Definitely Related:** A reaction that follows a reasonable temporal sequence from administration of study drug; that follows a known or expected response pattern to the study drug; it disappears or decreases on cessation or reduction in study drug dose; and/or it reappears or worsens when the study drug is administered.

**Probably Related:** A reaction that follows a reasonable temporal sequence from administration of study drug; that follows a known or expected response pattern to the study drug; and/or that could not be reasonably explained by other factors such as underlying disease, complications, concomitant drugs, or concurrent treatments.

**Possibly Related:** A reaction that follows a reasonable temporal sequence from administration of study drug; that follows a known or expected response pattern to the study drug, but that could reasonably have been produced by a number of other factors including underlying disease, complications, concomitant drugs, or concurrent treatments.

**Not Related:** A reaction for which sufficient data exist to indicate that the etiology is unrelated to the study drug.

### 8.2.3 Assessment of Outcome

The Investigator will record the outcome of the AE as either resolved or ongoing on the AE page of the eCRF. AEs of unknown outcome will be considered as ongoing for purposes of AE reporting.

## 8.3 ADVERSE EVENTS OF SPECIAL INTEREST

Adverse events of special interest (AESI) are those known to be attributed to parenteral amikacin:

Protocol Amendment #3 version: 22 February 2016

*This protocol is solely for the purpose of communicating information about the investigational drug between Insmmed Incorporated and study personnel. Information is not to be reproduced, abstracted or used for sharing of information for any other purpose, whatsoever, except with the written permission of Insmmed Incorporated.*

- nephrotoxicity, including elevation of serum creatinine, albuminuria, presence of red and white cells, casts, azotemia, and oliguria
- ototoxicity affecting the eighth cranial nerve resulting in hearing loss, loss of balance, or both.
- neuromuscular disorders
- allergic alveolitis
- bronchospasm
- hemoptysis

Cough is often associated with the drug products that are nebulized. In order to properly characterize AEs of cough, specific details regarding AE of cough will be reported in separate eCRF pages.

It is expected that patients in this study will experience a large number of pulmonary exacerbation events due to their underlying lung condition(s). Pulmonary exacerbation will be defined based on the Investigators best clinical judgment. Details of the type of exacerbation should be provided. These events should not be reported on the AE eCRF unless they meet the criteria for an SAE. Instead, these events should be reported in the “pulmonary exacerbation not SAE” page of the eCRF.

## **8.4 REPORTING REQUIREMENTS**

### **8.4.1 Adverse Events**

All AEs will be reported on the Adverse Events Form of the eCRF. Adverse events that occur between the time subject signs the informed consent form for the study and the time when subject receives his/her first dose of LAI or multi-drug regimen on Day 1 will be summarized as medical history and not as a treatment emergent AE (TEAE) unless the event meets the definition of an SAE as defined below.

Protocol Amendment #3 version: 22 February 2016

*This protocol is solely for the purpose of communicating information about the investigational drug between Insmmed Incorporated and study personnel. Information is not to be reproduced, abstracted or used for sharing of information for any other purpose, whatsoever, except with the written permission of Insmmed Incorporated.*

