- b The Screening window allows time for sputum culture results, minimum inhibitory concentration (MIC) determination, and scheduling of Screening assessments. Any delay in obtaining microbiological results and MICs must be reported to the Sponsor immediately and documented within the study source documents. In the event that sputum culture results are not known by 8 weeks (Day -14), the Baseline (Day 1) visit should be scheduled as soon as possible in order to maintain the Screening window, and an extension of the Screening window to 14 weeks is allowed, if necessary. If sputum culture results are known prior to 8 weeks (Day -14), the Screening window of 10 weeks must be maintained.
- c Serum pregnancy testing will be performed on women of child bearing potential at Screening. A urine pregnancy test will be performed on women of child bearing potential at all other visits. Women not of child bearing potential are defined as postmenopausal (i.e., amenorrheic for at least 1 year), or surgically or naturally sterile.
- d Vital signs and pulse oximetry will be assessed both before and after dosing on visits where study drug is administered.
- e The 6MWT must be conducted by a site member who is blinded to the subject’s open-label treatment assignment.
- f The PFTs will be performed at sites with access to spirometers and trained personnel to perform spirometry tests. See [Section 7.2.4](#).
- g The Baseline audiology examination must be performed during Screening period or on Day 1 before study drug administration.
- h At Baseline (Day 1), AEs will be assessed only after study drug administration or first dose of multi-drug regimen. Any AE that has occurred prior to the first dose must be included in the subject’s medical history, including any AEs that occur within the Screening period.
- i Only for subjects who agreed to participate in the CT Scan sub-study. A prior chest CT scan may be used as a subject’s Baseline (Day 1) measurement if this CT scan was obtained within 6 months from the subject’s Baseline (Day 1) visit. Subjects will have their follow-up chest CT scan at the EOT visit provided the last chest CT scan was not obtained within the prior 6 months. High resolution CT scan is preferred, if available. Please refer to [APPENDIX 4](#) for additional details on the CT Scan sub-study.

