#### **7.2.6 Adverse Events**

##### **7.2.6.1 Methodology**

AEs will be identified at every contact with a subject throughout the study period beginning with Day 1 and after first dose of LAI or multi-drug regimen by direct observation, from assessments of safety parameters, and by asking open-ended, non-leading questions such as “How have you felt since your last visit?” See [Section 8](#) for definitions and a fuller description of the assessment

Protocol Amendment #3 version: 22 February 2016

*This protocol is solely for the purpose of communicating information about the investigational drug between Insmmed Incorporated and study personnel. Information is not to be reproduced, abstracted or used for sharing of information for any other purpose, whatsoever, except with the written permission of Insmmed Incorporated.*

and reporting requirements of AEs. Any AE that is observed prior to first dose of LAI or multi-drug regimen will be classified as medical history.

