### 7.2.6.2 Assessment

All AEs will be recorded on the Adverse Event page of the eCRF. Attempts will be made to determine the start and stop dates of the event, the intensity, causality, treatment, and outcome of the event. Any AE that is observed prior to first dose of LAI or multi-drug regimen must be recorded on the Medical History page of the eCRF.

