## 8.4.2 Serious Adverse Events

All SAEs, regardless of causality, must be reported to organization delegated by the Sponsor (Primevigilance will handle SAE reporting for INS-212) on a Serious Adverse Event Report Form within 24 hours of becoming aware of the event; corrections and additions are required to be submitted within 24 hours. Study-specific email, phone, and fax number for SAE reporting are presented in the Study Reference Manual.

Unexpected drug-related SAEs as assessed by Sponsor or authorized person qualify for expedited reporting and will be reported to the IRB/EC, regulatory authorities, participating Investigators and, if cross reporting is required for suspected unexpected serious adverse reactions (SUSARs), in accordance with all applicable global laws and regulations. A SUSAR is a Serious Adverse Reaction, which is suspected to be caused by the investigational medicinal product and which is unexpected i.e. its nature or severity is not consistent with the information in the relevant source documents. SAEs, including those that do not meet requirements for expedited reporting, and all other AEs will be reported to the regulatory agencies as appropriate (i.e. for the FDA these are reported in the Investigational New Drug [IND] annual report and for EMA these are reported in the Drug Safety Update Report ([DSUR]).

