## **9.7 SAFETY ANALYSIS**

Safety data will be summarized for the Safety Population.

Adverse events will be coded using the agreed upon version of the Medical Dictionary for Regulatory Activities (MedDRA). For non-converters entering the single arm LAI study (Study INS-312), safety monitoring will continue as defined in that protocol. The number and percent of subjects with treatment emergent AEs by system organ class and preferred term will be presented by treatment arm. The severity of the AEs, the relationship to the investigational

Protocol Amendment #3 version: 22 February 2016

*This protocol is solely for the purpose of communicating information about the investigational drug between Insmmed Incorporated and study personnel. Information is not to be reproduced, abstracted or used for sharing of information for any other purpose, whatsoever, except with the written permission of Insmmed Incorporated.*

product, AEs causing study discontinuation, and all treatment emergent SAEs will be similarly presented. Fatal SAEs will also be presented separately in a similar manner.

Vital signs (temperature, systolic and diastolic blood pressure, pulse, pulse oximetry, and respiratory rate) results will be descriptively summarized by treatment arm.

Clinical laboratory test and pulmonary function results will be descriptively presented. Shifts of laboratory results from Baseline (Day 1) to Month 6 and EOT will be presented by treatment arm.

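### Section 8.4.1, read literally, counts an SAE before the first dose as treatment-emergent, while Sections 7.2.6.1 and 7.2.6.2 and Table 3-1 footnote h send every pre-dose AE to medical history

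*Protocol*

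**What the plan says.** **Pre-dose events.** Section 8.4.1 covers the time from signing consent to the first dose of LAI or multi-drug regimen on Day 1. Events in that interval "will be summarized as medical history and not as a treatment emergent AE (TEAE) unless the event meets the definition of an SAE". Three other places cover the same interval without an SAE exception:

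- Section 7.2.6.1: "Any AE that is observed prior to first dose of LAI or multi-drug regimen will be classified as medical history".
- Section 7.2.6.2: "Any AE that is observed prior to first dose of LAI or multi-drug regimen must be recorded on the Medical History page" of the eCRF.
- Table 3-1, footnote h, places pre-dose events in the subject's "medical history, including any AEs that occur within the Screening period".

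Section 8.4.2 adds a separate reporting duty: "All SAEs, regardless of causality, must be reported". Section 9.7 then sets out the tables that depend on the classification: "The number and percent of subjects with treatment emergent AEs by system organ class and preferred term will be presented by treatment arm", and "AEs causing study discontinuation, and all treatment emergent SAEs will be similarly presented".

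**Exacerbations.** Sections 7.2.6.2 and 8.4.1 each place all AEs on the AE page or form of the eCRF and state no exception. Section 8.3 says of pulmonary exacerbations: "These events should not be reported on the AE eCRF unless they meet the criteria for an SAE". It names a separate eCRF page for the non-serious ones, expects many of them, and leaves their definition to the investigator's judgment.

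**The concern.** The same event, an SAE during Screening, gets two classifications depending on the section followed. The exception in Section 8.4.1 is attached to how the event is summarized, so it bears on the safety tables as well as on expedited reporting. If it is followed, the treatment-emergent SAE tables include events from before any dose of LAI. Exclusion criterion 11 bars earlier LAI exposure, so LAI cannot have caused them. Adding the same background to both arms dilutes the relative comparison of SAE rates.

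For exacerbations, the general rule and Section 8.3 give opposite instructions about the AE form, and Section 9.7 does not mention the separate page. Safety tables built from the AE form alone would leave out the non-serious part of a respiratory event class that the protocol expects to be common. The trial is open-label, the drug is inhaled, and an investigator who may know the assigned arm decides what counts as an exacerbation and so which page is used.

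**Working it through.** **Step 1: the texts side by side.** For an SAE between consent and first dose:

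| Place | Classification | SAE exception? |
|---|---|---|
| 8.4.1 | Not confined to medical history; read literally, a TEAE | Yes |
| 7.2.6.1 | Medical history | No |
| 7.2.6.2 | Medical History page | No |
| Table 3-1, footnote h | Medical history, Screening period named | No |

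The four places cannot all be followed. Section 8.4.2 already requires every SAE to be reported, so limiting the clause in 8.4.1 would lose no reporting.

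**Step 2: effect on the tables of Section 9.7.** The protocol gives no figure to reproduce. Let r1 and r2 be the true treatment-emergent SAE proportions in the LAI and control arms, and p the chance of a pre-dose SAE. Assume p is independent of later events and equal in both arms, as randomization makes it in expectation. The tabulated proportion is then

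1 − (1 − r)(1 − p),

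and the tabulated difference is (1 − p)(r1 − r2). The difference shrinks by the fraction p. The ratio moves toward 1.

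**Step 3: illustration.** Section 1.3 gives SAE proportions of 18.2% and 8.9% for the double-blind phase of the earlier NTM study, which ended at Day 84. The values of p are assumptions. For 84 days, with no extrapolation:

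| p | LAI | Control | Ratio | Difference (points) |
|---|---|---|---|---|
| 0 | 18.2% | 8.9% | 2.04 | 9.3 |
| 1% | 19.0% | 9.8% | 1.94 | 9.2 |
| 5% | 22.3% | 13.5% | 1.66 | 8.8 |
| 10% | 26.4% | 18.0% | 1.46 | 8.4 |

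The minimum treatment period here is 8 months, about 243 days. At an assumed constant rate, r = 1 − (1 − r84)^(243/84), which gives 1 − 0.818^2.893 = 44.1% and 1 − 0.911^2.893 = 23.6%:

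| p | LAI | Control | Ratio | Difference (points) |
|---|---|---|---|---|
| 0 | 44.1% | 23.6% | 1.86 | 20.4 |
| 1% | 44.6% | 24.4% | 1.83 | 20.2 |
| 5% | 46.9% | 27.5% | 1.71 | 19.4 |
| 10% | 49.7% | 31.3% | 1.59 | 18.4 |

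**Step 4: how large p could be.** Applying the earlier study's placebo rate to the 70 to 98 days of Screening in Table 3-1 gives 1 − 0.911^(70/84) = 7.5% and 1 − 0.911^(98/84) = 10.3%. This is an upper end. Section 6.2 treats 70 days as a limit to be met, and exclusion criteria 20 and 22 may keep a subject with a Screening SAE from being randomized.

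**Step 5: exacerbations.** Under Section 8.1, worsening of an existing illness is an AE, so an exacerbation falls under the rule for all AEs. Section 8.3 takes the non-serious ones off that form. They are still captured, and Sections 8.2.1 and 8.2.2 call for intensity and causality for each AE. Section 8.2.3, however, has outcome recorded on the AE page, from which 8.3 removes them. The protocol gives no rate of non-serious exacerbations, so this part cannot be sized.

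**The case against.** **Intent of 8.4.1.** The clause sits directly before the SAE reporting rule of 8.4.2 and most likely means that SAEs are reported from consent onward. Lifting a medical-history rule does not by itself define a TEAE, and the ordinary meaning of treatment-emergent excludes pre-dose onset. Section 9.4 defers analysis details to the SAP, which is not shown and may define the term. All of this is fair and lowers the chance that the literal reading would be followed. It does not remove the conflict, because the exception still governs how an event is summarized and three places in the same protocol say otherwise.

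**Stronger readings of the first point.** A reader might infer that the rule would bias the arms against each other, or that it brings in events no study treatment could have caused. The documents support neither. Screening precedes randomization, so pre-dose events are balanced in expectation. Subjects may start or continue the multi-drug regimen at Baseline, so for those already on it a Screening SAE could be due to that regimen. Only LAI is ruled out.

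**Exacerbations.** Section 8.3 is a deliberate, specific instruction, and a site that reads it knows which page to use. That stands. A reader might infer that non-serious exacerbations are lost, or that they must go into the TEAE tables. They are recorded on their own page, serious ones remain on the AE form, and Section 9.7 does not restrict its tables to the AE form. A separate by-arm table would serve as well as a merge. What remains is that neither general rule acknowledges the exception and Section 9.7 is silent on the separate page.

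**Conclusion.** The point holds as a contradiction within the protocol about how a pre-dose SAE is classified, with a consequence for the treatment-emergent SAE tables if Section 8.4.1 is followed to the letter. The effect on the risk difference is small: at most about one tenth for p up to 10%. The ratio is more sensitive, falling in the 8-month illustration from 1.86 to between 1.83 (p = 1%) and 1.59 (p = 10%). These figures rest on an assumed p, equal and independent in both arms, on SAE rates from another trial, and on a constant rate beyond Day 84. They show direction and order of size and are not an estimate for this trial.

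The exacerbation point is secondary: an unacknowledged exception for an event class expected to be frequent, in an open-label trial of an inhaled drug. Both matters are worth correcting because the correction is cheap.

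**What to change.** 1. In Section 8.4.1, state that SAEs from consent onward are reported under 8.4.2, and that an event counts as treatment-emergent only if its onset or worsening is on or after the first dose of LAI or multi-drug regimen.
2. Align Sections 7.2.6.1 and 7.2.6.2 and Table 3-1 footnote h with that sentence.
3. In Sections 7.2.6.2 and 8.4.1, name the non-serious exacerbations of Section 8.3 as an express exception to the AE-form rule.
4. In Section 9.7, state that exacerbations from the separate page are summarized by treatment arm, either within the TEAE tables or in a table of their own.

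The cost is a few sentences, with no new visits or subjects. The downside is one more table, or higher exacerbation counts in the TEAE tables. The protocol does not show whether the separate page holds grade, causality and outcome, so the eCRF should be checked before choosing a merge. A separate by-arm table depends less on those fields.
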